5.6 Dosing for Phase II

Dosing for phase II will be administered as per Section 5.2. Dose of PD 0332991 will be 125 mg, which was the highest dose given in phase I (no MTD found). Thirty patients will

be enrolled to Arm 1 of phase II, 30 patients will be enrolled to Arm 2 of phase II, and 24 patients will be enrolled to Arm 3 of phase II. Enrollment for all arms may take place concurrently.

5.7 General Concomitant Medication and Supportive Care Guidelines

While taking PD 0332991, patients should be instructed to avoid food or drugs that are known strong CYP3A4 inhibitors or inducers. Patients should also refrain from the use of proton pump inhibitors; if needed, alternative antacid therapies may be used including H2-receptor antagonists, and locally acting antacids. H2-receptor antagonists should be administered with a staggered dosing regimen (twice daily). The dosing of PD 0332991 should occur at least 10 hours after the H2-receptor antagonist dose and 2 hours before the H2-receptor antagonist morning dose. Local antacid should be given at least 2 hours before or 2 hours after PD 0332991 administration.

Patients should receive full supportive care during the study, including transfusion of blood and blood products and treatment with antibiotics, analgesics, erythropoietin, or bisphosphonates when appropriate.

Anti-emetics (such as prochlorperazine, lorazepam, ondansetron, or other 5-HT3 antagonists) may be administered prophylactically in the event of nausea. Anti-diarrheals, such as loperamide, may be administered as needed in the event of diarrhea.

5.8 Women of Childbearing Potential

Women of childbearing potential (defined as women with regular menses, women with amenorrhea, women with irregular cycles, women using a contraceptive method that precludes withdrawal bleeding, and women who have had a tubal ligation) are required to have a negative serum pregnancy test within 28 days prior to the first dose of study treatment.

Female and male patients (along with their female partners) are required to use two forms of acceptable contraception, including one barrier method, during participation in the study and for 3 months following the last dose of PD 0332991.

If a patient is suspected to be pregnant, all study drugs should be immediately discontinued. In addition a positive urine test must be confirmed by a serum pregnancy test. If it is confirmed that the patient is not pregnant, the patient may resume dosing.

If a female patient or female partner of a male patient becomes pregnant during therapy or within 28 days after the last dose of either study drug, the investigator must be notified in order to facilitate outcome follow-up.

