 - d. Total bilirubin ≤ 1.5 x IULN except in the case of patients with Gilbert's disease
 - e. AST (SGOT) and ALT (SGPT) ≤ 2.5 x IULN for patients without liver metastases and ≤ 5.0 x IULN for patients with liver metastases
 - f. Alkaline phosphatase ≤ 2.5 x IULN for patients without bone metastases and ≤ 5.0 x IULN for patients with bone metastases

- g. Serum creatinine $\leq 1.5 \times$ IULN OR calculated creatinine clearance ≥ 50 mL/min/1.73 m² for patients with creatinine levels above institutional normal
13. Baseline corrected QT interval (QTc) < 480 ms.
14. Women of childbearing potential and men must agree to use adequate contraception (hormonal or barrier method of birth control, abstinence) prior to study entry and for the duration of study participation. Should a woman become pregnant or suspect she is pregnant while participating in this study, she must inform her treating physician immediately.
15. Available archival tumor tissue for the proposed correlative studies.
16. Ability to understand and willingness to sign an IRB approved written informed consent document (or that of legally authorized representative, if applicable).

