3.2 Exclusion Criteria

1. Phase II, Arm 1 only: prior treatment with cetuximab.
2. A history of other malignancy ≤ 1 year previous with the exception of basal cell or squamous cell carcinoma of the skin which were treated with local resection only, carcinoma *in situ* of the cervix, or synchronous H&N primaries.
3. Currently receiving any other investigational agents.
4. Patient must not have a history of or clinical evidence of central nervous system metastases or leptomeningeal carcinomatosis, except for individuals who have had previously-treated CNS metastases, are asymptomatic, and have had no requirement for steroids or anti-seizure medications (with the exception of Keppra) for 1 month prior to first dose of PD 0332991.
5. A history of allergic reactions attributed to compounds of similar chemical or biologic composition to PD 0332991, cetuximab, or other agents used in the study.
6. Treated within the last 7 days prior to Day 1 of protocol therapy with:
 - a. Food or drugs that are known to be CYP3A4 inhibitors (e.g. grapefruit juice, verapamil, ketoconazole, miconazole, itraconazole, erythromycin, clarithromycin, telithromycin, indinavir, ritonavir, nelfinavir, atazanavir, amprenavir, nefazodone, diltiazem, and delavirdine) or inducers (i.e. dexamethasone, glucocorticoids, progesterone, rifampin, phenobarbital, St. John's wort). (See Appendix D)
 - b. Drugs that are known to prolong the QT interval.
 - c. Drugs that are proton pump inhibitors.
7. Uncontrolled electrolyte disorders that can compound the effects of a QTc-prolonging drug (e.g., hypocalcemia, hypokalemia, hypomagnesemia)

8. Uncontrolled intercurrent illness including, but not limited to, ongoing or active infection symptomatic congestive heart failure, unstable angina pectoris, cardiac arrhythmia, or psychiatric illness/social situations that would limit compliance with study requirements.
9. Pregnant and/or breastfeeding. Women of childbearing potential must have a negative serum pregnancy test within 28 days of study entry. Female patients must be surgically sterile or be postmenopausal, or must agree to use effective contraceptive during the period of the trial and for at least 90 days after completion of treatment. The decision of effective contraception will be based on the judgment of the principal investigator or a designated associate.

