7.8 Timeframe for Reporting Required Events

Adverse events will be tracked for 30 days following the last day of study treatment.

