8.1.9 Pregnancy

The nonclinical safety profile of palbociclib has been well characterized through the conduct of single- and repeat-dose toxicity studies up to 39 weeks in duration, and safety pharmacology, genetic toxicity, reproductive and developmental toxicity, and phototoxicity studies. Consistent with the pharmacologic activity of palbociclib (cell cycle inhibition, CDK4/6 inhibition), the primary target organ findings included hematolymphopoietic (decreased cellularity of bone marrow and lymphoid organs) and male reproductive organ (seminiferous tubule degeneration, and secondary effects on the epididymis, prostate, and seminal vesicle) effects in rats and dogs, and altered glucose metabolism that was accompanied by effects on the pancreas and secondary changes in the eye, teeth, kidney, and adipose tissue in rats only, and effects on bone in rats only that were observed following single and/or repeat dosing at clinically relevant exposures. Altered glucose metabolism (hyperglycemia/glucosuria) correlated with pancreatic islet cell vacuolation that was determined to reflect a loss of beta cells with corresponding decreases in insulin and C-peptide. The reversibility of the effects on glucose homeostasis, pancreas, eye, kidney, and bone was not established following a 12-week non-dosing period; whereas partial to full reversal of effects on the hematolymphopoietic and male reproductive systems, teeth, and adipose tissue were observed. Additionally, a potential for QTc prolongation and hemodynamic effects were identified from safety pharmacology studies, and developmental toxicity was identified from embryo-fetal development studies in the rat and rabbit. Though gastrointestinal effects would be anticipated from a cell cycle inhibitor and while effects were observed in rats and dogs following single- and repeat-dose studies up to 3 weeks in duration (emesis, fecal changes, and microscopic changes in stomach and intestines), the effects were of limited severity at clinically relevant doses. Gastrointestinal effects were not prominent in longer duration studies, limited to effects on the glandular stomach and rodent-specific effects on the non-glandular stomach in rats following 27 weeks of intermittent dosing that did not reverse during a 12-week non-dosing period. Additional palbociclib-related findings considered non-adverse at tolerated doses based on limited severity and/or absence of degenerative changes included cellular vacuolation in multiple tissues that was morphologically consistent with phospholipidosis; hepatic (increases in liver enzymes, hepatocellular hypertrophy/increased vacuolation), renal (increased CPN), adrenal (cortical cell hypertrophy), and respiratory (clinical signs, tracheal epithelial cell atrophy) effects; and prolonged coagulation times. Reversibility (partial or full) was established for these additional toxicities. Finally, palbociclib was determined to be an aneugen, for which a no effect exposure was identified

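### Section 5.8 requires contraception for 3 months after the last PD 0332991 dose but pregnancy notification for only 28 days, and the contraception rules disagree

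*Combined protocol and SAP*

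**What the plan says.** Three passages set contraception rules.

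- **Section 5.8** asks female patients, and male patients with their female partners, for two forms including a barrier, "during participation in the study and for 3 months following the last dose of PD 0332991".
- **Section 3.2, exclusion criterion 9** applies to female patients who are neither surgically sterile nor postmenopausal. It runs through the trial and "for at least 90 days after completion of treatment", and leaves the method to the judgment of the principal investigator or a designee.
- **Section 3.1, inclusion criterion 14** covers women of childbearing potential and men. It accepts a single method, "prior to study entry and for the duration of study participation", with no post-treatment period. It also tells a woman who becomes or may be pregnant during her participation to inform her physician at once.

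Section 5.8 then sets the notification rule. For a female patient or a male patient's partner, it applies to a pregnancy that begins on treatment or "within 28 days after the last dose of either study drug, the investigator must be notified"; the stated purpose is to follow the outcome.

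Section 7.7 makes exposure to PD 0332991 in pregnancy or lactation reportable to the drug supplier, with no end date in that sentence. Section 7.8 states: "Adverse events will be tracked for 30 days following the last day of study treatment". In the Section 10 calendar the last pregnancy test is at end of treatment. Footnote j limits later checks to recurrence and survival, every 2 months for 5 years, and allows them by phone or record review.

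**The concern.** Section 5.8 asks patients and partners to avoid conception for 3 months, yet asks to hear of a failure only in roughly the first third of that time. A conception between day 29 and day 90 would breach the contraception rule without triggering the notification rule.

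What could be lost is outcome information. Section 7.1.2 counts a congenital anomaly or birth defect as a serious outcome. Such an outcome appears months after conception, so a 30-day adverse event window cannot be relied on to find it. The investigator can report to the supplier under Section 7.7 only what the investigator learns.

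Section 8.1.9 gives some reason to want these outcomes. It reports developmental toxicity in rat and rabbit, and degeneration in the male reproductive tract with partial to full reversal after a 12-week non-dosing period. It also says "palbociclib was determined to be an aneugen", with the qualification that a no-effect exposure was identified. The male findings make partners of male patients the clearest group at issue.

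**Working it through.** The plan states no figure here to reproduce. The check is interval arithmetic plus a comparison of passages.

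**1. Post-treatment days outside the notification window, same start day**

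Uncovered days = contraception window − 28; share = uncovered days ÷ contraception window.

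- 90 days (exclusion criterion 9): 90 − 28 = 62; 62/90 = 68.9%.
- 3 calendar months (Section 5.8), taken as 89 to 92 days: 61/89 = 68.5% to 64/92 = 69.6%.

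**2. Different anchors**

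The contraception window in Section 5.8 runs from the last PD 0332991 dose, and the notification window from the last dose of either drug. Assume the 28 days run from the later drug and cetuximab ends g days after PD 0332991. Then uncovered days = max(0, 90 − 28 − g).

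| g (days) | Uncovered days | Share of 90 |
|---|---|---|
| 0 | 62 | 69% |
| 1 | 61 | 68% |
| 7 | 55 | 61% |
| 14 | 48 | 53% |
| 28 | 34 | 38% |
| 62 or more | 0 | 0% |

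The protocol does not say that the later drug is meant. Exclusion criterion 9 counts from completion of treatment. If that means both drugs, its start moves with the notification window and the gap stays at 62 of 90 for female patients.

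**3. On-treatment time included**

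Pregnancies during therapy are covered. With T days on treatment, the uncovered share of treatment plus 90 days is 62/(T + 90):

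- one 28-day cycle: 62/118 = 52.5%;
- two cycles: 62/146 = 42.5%;
- six cycles: 62/258 = 24.0%.

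**4. Does another visible passage close the gap?**

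- Inclusion criterion 14: a real duty, but on women only and tied to participation. Section 5.8 lists participation and the 3 months after the last dose as separate periods, which suggests that the post-treatment months are not part of participation.
- Section 7.7: exposure in pregnancy is reportable, but no one is told to inform the investigator of a conception after day 28. Its serious adverse event period refers to a Section 7.9, and Section 7 ends at 7.8.
- Section 7.8: 30 days, which leaves 60 of 90 (67%).
- Calendar footnote j: pregnancy is not among the follow-up items.

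**5. Contraception passages side by side**

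| Place | Who | Method | End |
|---|---|---|---|
| Inclusion 14 | women of childbearing potential, men | single method accepted | end of participation |
| Exclusion 9 | women | investigator's judgment | at least 90 days after treatment |
| Section 5.8 | women; men with partners | two forms, one a barrier | 3 months after PD 0332991 |

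**The case against.** The two windows need not be equal. A contraception period can carry a precautionary margin, while notification can follow drug exposure. Section 1.5 gives PD 0332991 a mean half-life of 25.9 hours, so 28 days is 672/25.9 = about 26 half-lives. Section 8.2.3 gives cetuximab about 112 hours (range 63 to 230), so 28 days is 6 half-lives at the mean and 672/230 = 2.9 at the upper end. A woman who conceives after day 28 would have essentially no PD 0332991 in plasma. This stands as far as it goes: the protocol never labels the 3 months a risk period, so a reader who infers that it declares one, and that 28 days is therefore wrong, goes beyond the text. The argument is weaker for conceptions fathered by male patients, where the Section 8.1.9 findings concern the reproductive organs, and reversal was not complete for every effect.

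A reader might also infer that no pregnancy after day 28 could ever be captured. The documents do not support that. Inclusion criterion 14 creates a second disclosure duty, and its reference to participation might be read to include the 5-year follow-up. Part of Section 8.1.9, Appendix C (the supplier's report sheet) and the consent form were not available for this check, and any of them could carry pregnancy-reporting wording.

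Finally, a patient who follows the fuller rule in Section 5.8 would also satisfy inclusion criterion 14 as to duration. That is fair, but a man reading only the eligibility criteria would see no post-treatment period at all.

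**Conclusion.** The mismatch is real and lies within one section. The 69% figure applies to the post-treatment contraception period and assumes a common start day. It falls, possibly to zero, if cetuximab outlasts PD 0332991 and the 28 days run from the later drug. The larger claim that most of the whole period of possible exposure is uncovered fails once treatment time is counted, except after very short treatment.

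The visible text does not close the gap, and closes it least for partners of male patients. The disagreement among the three contraception passages is separate but belongs in the same correction. The documents do not show which contraception rule is intended, and none is favoured here.

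This is a safety-capture and consistency point. Few pregnancies are expected, and nothing in it touches the response endpoint, the sample sizes or the stopping boundaries.

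**What to change.** 1. Reconcile inclusion criterion 14, exclusion criterion 9 and Section 5.8 on contraception method, end date and the drug from which the period is counted. The choice is the sponsor's.
2. In Section 5.8, set the pregnancy notification window to the same post-treatment period and anchor, and state that it covers female patients and partners of male patients. Say whether a period counted from either drug means the earlier or the later last dose.
3. In calendar footnote j, add a pregnancy question at each follow-up check within that period and at the first check after it. With checks every 2 months from end of treatment, a 3-month period would contain only the first, at about 2 months; a later conception would surface at about 4 months.

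The text changes are small: a phrase in Section 5.8, a line in footnote j, aligned eligibility wording and matching consent language. The practical cost is somewhat larger. Record review would not reliably show a partner's pregnancy, so those one or two checks would need a brief phone contact.

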5.9 Duration of Therapy

If at any time the constraints of this protocol are considered to be detrimental to the

patient's health and/or the patient no longer wishes to continue protocol therapy, the protocol therapy should be discontinued and the reason(s) for discontinuation documented in the case report forms.

In the absence of treatment delays due to adverse events, treatment may continue indefinitely until one of the following criteria applies:

- Documented and confirmed disease progression
- Death
- Adverse event(s) that, in the judgment of the investigator, may cause severe or permanent harm or which rule out continuation of study drug
- General or specific changes in the patient's condition render the patient unacceptable for further treatment in the judgment of the investigator
- Suspected pregnancy
- Serious non-compliance with the study protocol
- Lost to follow-up
- Patient withdraws consent
- Investigator removes the patient from study
- The Siteman Cancer Center decides to close the study

Patients who prematurely discontinue treatment for any reason will be followed as indicated in the study calendar.

5.10 Duration of Follow-up

Patients will be followed every 2 months for 5 years or until death, whichever occurs first. Patients removed from study for unacceptable adverse events will be followed until resolution or stabilization of the adverse event.

6.0 DOSE DELAYS/DOSE MODIFICATIONS

6.1 Dose Modifications for PD 0332991

Patients will be monitored for toxicity and the dose of PD 0332991 may be adjusted as indicated in the table below. Dose reduction by 1, and if possible, 2 dose levels will be allowed depending on the type and severity of toxicity encountered. Patients requiring more than 2 dose reductions will be discontinued from the study.

Recommended dose reductions for PD 0332991 are to decrease the current dose by 25 mg. The lowest dose available is 75 mg. Doses may be held as needed for toxicity resolution during a cycle. Doses omitted for toxicity are not replaced or restored within the same cycle (meaning that the cycle remains 28 days regardless of the number of doses of taken).

If a patient experiences a toxicity which has not resolved to grade 2 or lower within two weeks (inclusive of the scheduled off-week), treatment with PD 0332991 should be

permanently discontinued.

PD 0332991 Dose Modifications Based on Worst Treatment-Related Toxicity in the Previous Cycle

Worst Toxicity During Previous Cycle	New Dose Level
Grade 4 neutropenia	Decrease by one dose level
Grade 4 thrombocytopenia	Decrease by one dose level
Grade 3 neutropenia associated with a documented infection or fever ≥ 38.5 °C	Decrease by one dose level
Grade ≥ 3 non-hematologic toxicity (includes nausea, vomiting, diarrhea, and hypertension only if persisting despite maximal medical treatment)	Decrease by one dose level
Delay by > 1 week in receiving the next scheduled dose due to persisting treatment-related toxicities	If recovery occurs within 2 weeks, continue and decrease by one dose level
Inability to deliver at least 80% of the planned dose of PD 0332991 due to adverse events possibly related to study treatment	Decrease by one dose level

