5.3 Re-Treatment Criteria

A new cycle of treatment with PD 0332991 may begin only if:

- ANC \geq 1,000/mcL.
- Platelets count \geq 50,000/mcL.
- Non-hematologic toxicities have returned to baseline or no greater than grade 1 (or no greater than grade 2 if not considered a safety risk for the patient (at the investigator's discretion)).

If these conditions are not met, treatment with PD 0332991 must be delayed by one week. If, after a one-week delay, all toxicities have recovered within the limits described above, treatment with PD 0332991 can be resumed.

If the patient has not recovered after 2 weeks (including the scheduled 1-week off treatment period within a cycle), treatment with PD 0332991 will be permanently discontinued.

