5.4 Dose Escalation Schema for Phase I

Dose Escalation Schedule (for the Phase I portion)		
Dose Level	PD 0332991 Dose*	Cetuximab Dose
Level -1	75 mg	Loading dose: 400 mg/m ²
Level 1 (Starting Dose)	100 mg	Weekly thereafter: 250 mg/m ² for
Level 2	125 mg	the duration of study participation

* PD 0332991 is administered on Days 1 through 21 of each 28-day cycle.

Dose escalation will not occur until all patients in the cohort have completed the first cycle and the Principal Investigator has been able to review all toxicities.

5.5 Definition of MTD, DLT, Dose Escalation Criteria, and Toxicity, Response, and DLT Evaluations for Phase I

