5.5.4 Toxicity, Response, and DLT Evaluations

All patients who receive any study treatment are evaluable for toxicity. Patients are evaluated from first receiving study treatment until a 30-day follow up after the conclusion of treatment or death.

All patients are evaluable for disease response unless they come off study due to treatment related adverse events(s) prior to completion of Cycle 2 and have not had any disease assessment.

A patient is evaluable for DLT assessment only during Cycle 1 of treatment and only if enrolled in phase I of the trial. If the patient is not able to be treated on Day 1 of Cycle 2, then s/he is still considered in Cycle 1 active treatment and can experience a DLT. Once the patient has been treated in Cycle 2, s/he will no longer be evaluated for DLTs in all subsequent cycles.

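### For a delay at a cycle start, the delay row in the Section 6.1 table either contradicts the two-week stopping rule for PD 0332991 or can never apply, and Sections 5.3 and 6.1 state different recovery grades

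*Combined protocol and SAP*

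**What the plan says.** The schedule in Section 5.4 is "PD 0332991 is administered on Days 1 through 21 of each 28-day cycle", which leaves a 7-day off-week before the next dose is due.

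Three statements then deal with toxicity that has not cleared:

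- **Section 5.3.** A new cycle needs minimum neutrophil and platelet counts, and non-hematologic toxicities must "have returned to baseline or no greater than grade 1". Grade 2 is accepted if the investigator sees no safety risk. If the conditions are not met, "treatment with PD 0332991 must be delayed by one week". The end point is reached as follows: "If the patient has not recovered after 2 weeks (including the scheduled 1-week off treatment period within a cycle"), at which point PD 0332991 stops for good.
- **Section 6.1, paragraph.** PD 0332991 is to stop permanently if a toxicity "has not resolved to grade 2 or lower within two weeks", again with the off-week counted.
- **Section 6.1, table.** One row applies when persisting treatment-related toxicity makes the next scheduled dose more than a week late. Its action is "If recovery occurs within 2 weeks, continue and decrease by one dose level".

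Section 5.5.4 is relevant to a possible consequence. Patients are evaluable for response "unless they come off study due to treatment related adverse events(s) prior to completion of Cycle 2" and have had no disease assessment.

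**The concern.** The two paragraphs stop the drug at a point that the table row treats as still open. The row does not say when its two weeks begin, and no section says which statement takes precedence. Two investigators following the protocol in good faith could therefore stop one patient and continue an identical one at a lower level. What is at stake is patient safety and consistent exposure to PD 0332991 in a trial that provides for several sites (Section 16). The differing recovery grades add a second, weaker uncertainty at the same time point.

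**Working it through.** The plan gives no figure to reproduce, so the check is calendar arithmetic on the 21-days-on, 7-days-off schedule.

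**Inputs.** The off-week is 28 − 21 = 7 days (Section 5.4). The stopping clock is 14 days including the off-week (Section 5.3 and the Section 6.1 paragraph). The row's trigger is a next dose more than 7 days late, and its recovery window is 14 days from an unstated start (Section 6.1 table).

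**Step 1: the stopping clock as days late.** At a cycle start, drug-free days = 7 + days past the due date. Setting drug-free days to 14 gives 14 − 7 = 7 days past due. Both paragraphs agree on this.

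**Step 2: where the row begins.** More than 7 days past due means more than 7 + 7 = 14 drug-free days. The row opens only after the stopping clock has run out.

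**Step 3: where the row ends.**

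| Start of the row's two weeks | Drug-free days on which recovery still allows continuation | Result at a cycle start |
|---|---|---|
| Due date | up to 14 + 7 = 21 | Drug-free days 15 to 21 (8 to 14 days late): stopped by the paragraphs, continued by the row |
| First day of the off-week | up to 14 | The trigger needs more than 14, so no patient can meet the row |

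**Step 4: a test patient.** Non-hematologic toxicity is grade 3 at drug-free day 14 and grade 1 at day 17, which is 17 − 7 = 10 days late.

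- Section 5.3: not recovered at day 14, so stopped.
- Section 6.1 paragraph: above grade 2 at day 14, so stopped.
- Section 6.1 table, counted from the due date: more than 7 days late and recovered within 14, so continued at a reduced level.

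Section 6.1 therefore also conflicts with itself.

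**Step 5: the recovery grade at day 14.** Take non-hematologic toxicity that is grade 2 and judged a safety risk. Section 5.3 stops the drug. The Section 6.1 paragraph is not triggered, because grade 2 has been reached, and it gives no further instruction for this patient. The paragraphs differ in strictness but do not give opposite orders.

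**Step 6: is the row confined to holds within a cycle?** Section 6.1 does not say so. The table sets the new level from the worst toxicity of the preceding cycle, and the text describes doses held during a cycle as omitted and not replaced. A hold of at least 8 of the 21 dosing days delivers at most 13/21 = 62% of the planned dose. When the adverse event is possibly related to treatment, the separate row for delivering less than 80% already covers such a hold.

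**The case against.** The best defense is that the row refers to the next scheduled dose and not to the next cycle. PD 0332991 is taken daily and may be held during a cycle. A mid-cycle hold of more than 7 days that clears within 14 days meets the row and breaches neither paragraph, and Section 5.3 concerns only the start of a new cycle. This reading is possible, and it would remove the clock conflict. It does not settle the matter, because the row is not restricted to such holds and its start point is not given.

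A second objection is that the two recovery grades are compatible, and this stands. A reader might infer that Section 6.1 keeps a patient on treatment whenever toxicity is grade 2, so that the sections give opposite outcomes. The text does not say that. It makes failure to reach grade 2 a reason to stop, without saying that it is the only reason. A site can obey both paragraphs by applying the stricter, and Section 5.9 separately lets the investigator stop for adverse events. What remains is that nothing says which grade governs.

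A reader might also infer that the conflict changes the response-rate denominator and could decide an arm. The documents do not support this as a general statement. Sections 5.3 and 6.1 end PD 0332991, whereas Section 5.5.4 excludes patients who come off study. Section 6.1 words the two separately: more than two dose reductions removes a patient from the study, while unresolved toxicity ends the drug. The exclusion also requires leaving before Cycle 2 is completed and having no disease assessment.

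**Conclusion.** The clock conflict holds and the protocol is wrong as written on this point. For a delay at a cycle start, the table row either contradicts Section 5.3 and the Section 6.1 paragraph for recovery 8 to 14 days past the due date, or it has no patients to apply to. The conclusion rests on the 21/7 schedule and on the row not being limited to holds within a cycle.

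The difference in recovery grade is a real but lesser ambiguity. It is shown here for non-hematologic toxicity only, and no conflict has been shown for the neutrophil and platelet limits in Section 5.3.

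The documents do not give the number of patients with such a delay. Any effect on the response-evaluable set depends on stopping PD 0332991 counting as coming off study, before Cycle 2 is completed and without an assessment. The documents do not state this, and the size of the effect cannot be derived. Assuming a number of excluded patients would measure the exclusion in Section 5.5.4 itself, not the difference between the readings.

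**What to change.** Reconcile Section 5.3, the Section 6.1 paragraph and the Section 6.1 table row so that they give:

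1. one delay clock, with its start point and its length stated;
2. one recovery grade at the end of that clock;
3. the scope of the row: delays at a cycle start, holds within a cycle, or both.

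The choice of rule belongs to the sponsor's clinicians, and this review takes no position on it. In the same amendment, it would help to state in Section 5.5.4 whether ending PD 0332991 alone counts as coming off study, which would settle the conditional link to response evaluability. The cost is protocol wording in two sections, plus one sentence if that clarification is added. Sample size and decision rules need no change.
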